6.2 Dose modifications

6.2.1 Dose adjustment and interruption

Treatment with everolimus and exemestane should continue as long as clinical benefit is observed or until unacceptable toxicity occurs. The management of severe and/or intolerable suspected adverse events may require temporary dose interruption (with or without dose reduction) or discontinuation of everolimus therapy.

Dose adjustments are permitted for any adverse event suspected to be related to everolimus in those patients unable to tolerate their individual once daily oral dose. If dose reduction is required, the suggested dose is approximately 50% lower than the daily dose previously administered (see Table 6-2).

If administration of everolimus must be interrupted because of unacceptable toxicity, everolimus dosing should be interrupted or modified according to the guidelines presented in Table 6-2, [Table 6-3](#), and [Table 6-4](#).

Table 6-2 Everolimus dose reduction steps

Dose level	Dose and schedule
0 = starting dose	10 mg daily
-1 dose level	5 mg daily
-2 dose level	5 mg every other day

In addition, if any surgery is planned, everolimus dosing should be interrupted one week prior to surgery and should be re-started as soon as possible after wound healing.

[figure not shown]

Table 6-3 and Table 6-4 provide the procedure to be followed in the event of toxicities suspected to be related to the everolimus treatment. Included are also instructions for re-initiation of everolimus dosing once sufficient recovery of toxicity is seen. If everolimus dosing is interrupted due to toxicity, everolimus should not be resumed unless recovery to grade ≤ 1 is achieved in less than 4 weeks. Then everolimus could be reintroduced at the initial dose or a lower dose level depending on the toxicity type and grade (see Table 6-3 and Table 6-4).

If a patient has already decreased everolimus intake by 2 dose levels, no further dose reduction is permitted. Patients requiring an additional everolimus dose reduction will be required to discontinue study treatment. Patients who interrupt everolimus therapy for more than 4 weeks must be discontinued from the study.

All study drugs, i.e. everolimus and exemestane, interruptions or dose modifications must be recorded on the Dosage Administration Record page of the CRF.

Table 6-3 Everolimus: dose modification guidelines for hematologic toxicities

Toxicity	Actions
Thrombocytopenia / Platelet count	$\geq 75000/\text{mm}^3$: No change $50000/\text{mm}^3$ to $75000/\text{mm}^3$ Hold everolimus treatment until recovery to $\geq 75000/\text{mm}^3$. Reintroduce everolimus at the same dose level $< 50000/\text{mm}^3$ Hold everolimus treatment until recovery to $\geq 75000/\text{mm}^3$. Reintroduce everolimus at the next lower dose level, if available.
Absolute neutrophil count (ANC)	$\geq 1000/\text{mm}^3$: No change $500/\text{mm}^3$ to $1000/\text{mm}^3$ Hold everolimus treatment until recovery to $\geq 1000/\text{mm}^3$. Reintroduce everolimus at the same dose level $< 500/\text{mm}^3$ Hold until recovery to $\geq 1000/\text{mm}^3$. Reintroduce everolimus (at the next lowest dose level, if available.
Febrile neutropenia	Hold further dosing until $\text{ANC} \geq 1250/\text{mm}^3$ and no fever. Then resume dosing at the next lower dose level, if available.
Toxicity requiring interruption for > 4 weeks	Permanently discontinue treatment.
Physicians should always manage patients according to their medical judgment based on the particular clinical circumstances.	

Table 6-4 Everolimus: dose modification guidelines for non-hematologic toxicities

Adverse drug reaction	Severity	Everolimus dose adjustment and management recommendations
Non-infectious pneumonitis	Grade 1 Asymptomatic, radiographic findings only	No dose adjustment required. Initiate appropriate monitoring.
	Grade 2 Symptomatic, not interfering with ADL	Consider interruption of therapy, rule out infection and consider treatment with corticosteroids until symptoms improve to \leq grade 1. Re-initiate everolimus at a lower dose. Discontinue treatment if failure to recover within 4 weeks.
	Grade 3 Symptomatic, interfering with ADL; O ₂ indicated	Interrupt everolimus until symptoms resolve to \leq grade 1. Rule out infection, and consider treatment with corticosteroids. Consider re-initiating everolimus at a lower dose. If toxicity recurs at Grade 3, consider discontinuation.
	Grade 4 Life-threatening, ventilatory support indicated	Discontinue everolimus Rule out infection Consider treatment with corticosteroids.
Stomatitis ^a	Grade 1 Minimal symptoms, normal diet	No dose adjustment required. Manage with non-alcoholic or salt water (0.9%) mouth wash several times a day.
	Grade 2 Symptomatic but can eat and swallow modified diet	Temporary dose interruption until recovery to grade \leq 1. Re-initiate everolimus at the same dose. If stomatitis recurs at grade 2, interrupt dose until recovery to grade \leq 1. Re-initiate everolimus at a lower dose. Manage with topical analgesic mouth treatments (e.g. benzocaine, butyl aminobenzoate, tetracaine hydrochloride, menthol or phenol) with or without topical corticosteroids (i.e. triamcinolone oral paste).
	Grade 3 Symptomatic and unable to adequately eat or hydrate orally	Temporary dose interruption until recovery to grade \leq 1. Re-initiate everolimus at a lower dose. Manage with topical analgesic mouth treatments (i.e. benzocaine, butyl aminobenzoate, tetracaine hydrochloride, menthol or phenol) with or without topical corticosteroids (i.e. triamcinolone oral paste)
	Grade 4 Symptoms associated with life-threatening consequences	Discontinue everolimus and treat with appropriate medical therapy.
Other non-hematologic toxicities (excluding metabolic events)	Grade 1	If toxicity is tolerable, no dose adjustment required. Initiate appropriate medical therapy and monitor.
	Grade 2	If toxicity is tolerable, no dose adjustment required. Initiate appropriate medical therapy and monitor. If toxicity becomes intolerable, temporary dose interruption until recovery to grade \leq 1. Re-initiate everolimus at the same dose. If toxicity recurs at grade 2, interrupt everolimus until recovery to grade \leq 1. Re-initiate everolimus at a lower dose.

Adverse drug reaction	Severity	Everolimus dose adjustment and management recommendations
	Grade 3	Temporary dose interruption until recovery to grade ≤1. Initiate appropriate medical therapy and monitor. Consider re-initiating everolimus at a lower dose. If toxicity recurs at grade 3, consider discontinuation.
	Grade 4	Discontinue everolimus and treat with appropriate medical therapy.
Metabolic events (e.g. hyperglycemia, dyslipidemia)	Grade 1	No dose adjustment required. Initiate appropriate medical therapy and monitor.
	Grade 2	No dose adjustment required. Manage with appropriate medical therapy and monitor.
	Grade 3	Temporary dose interruption. Re-initiate everolimus at a lower dose. Manage with appropriate medical therapy and monitor.
	Grade 4	Discontinue everolimus and treat with appropriate medical therapy.
Toxicity requiring interruption for > 4 weeks		Permanently discontinue treatment
ADL: activities of daily living O2: oxygen ^a : Avoid using agents containing hydrogen peroxide, iodine, and thyme derivatives in management of stomatitis as they may worsen mouth ulcers. Severity grade description: 1 = mild symptoms; 2 = moderate symptoms; 3 = severe symptoms; 4 = life-threatening symptoms. If dose reduction is required, the suggested dose is approximately 50% lower than the dose previously administered.		

6.2.2 Follow-up for toxicities

[figure not shown]
Patients whose everolimus treatment is interrupted or permanently discontinued due to an adverse event or abnormal laboratory value suspected to be related to study treatment must be followed at least weekly until the adverse event or abnormal laboratory values resolves or returns to grade 1.

If a patient requires a dose delay of > 4 weeks from the intended day of the next scheduled dose for either everolimus or exemestane, then the patient must be discontinued from the study.

6.3 Known undesirable effects of the study drugs

The most frequently observed adverse events (AEs) with everolimus are rash, stomatitis /oral mucositis, non-infectious pneumonitis, fatigue, headache, anorexia, nausea, vomiting, diarrhea, and infections. Overall, the most frequently observed laboratory abnormalities include neutropenia, thrombocytopenia, hypercholesterolemia, and/or hypertriglyceridemia. The majority of these AEs have been of mild to moderate severity (NCI CTC grade 1-2).

Recommendations for dose adjustments, should any of these treatment-related adverse events occur, are given in [Table 6-2](#), [Table 6-3](#), and [Table 6-4](#).

The most frequently reported adverse effects for exemestane are gastrointestinal disturbances, hot flushes, arthralgia, myalgia, sweating, fatigue and dizziness. Other reported effects include headache, insomnia, somnolence, depression, skin rashes, alopecia, asthenia and leg oedema. Thrombocytopenia and leucopenia have been reported occasionally. Reductions in bone mineral density can occur with long-term use of exemestane ([Motzer 2008](#)).

Please refer to the package insert of the local supply of exemestane for more details.

6.3.1 Non-infectious pneumonitis

Non-infectious pneumonitis is a class effect of rapamycin derivatives. Cases of non-infectious pneumonitis (including interstitial lung disease) have also been described in patients taking everolimus. Some of these have been severe and on rare occasions, a fatal outcome was observed.

A diagnosis of non-infectious pneumonitis should be considered in patients presenting with non-specific respiratory signs and symptoms such as hypoxia, pleural effusion, cough or dyspnea, and in whom infectious, neoplastic and other non-medicinal causes have been excluded by means of appropriate investigations. Opportunistic infections such as PJP should be considered ruled out in the differential diagnosis of non-infectious pneumonitis. Patients should be advised to report promptly any new or worsening respiratory symptoms.

Patients who develop radiological changes suggestive of non-infectious pneumonitis and have few or no symptoms may continue everolimus therapy without dose alteration. If symptoms are moderate (grade 2), consideration should be given to interruption of therapy until symptoms improve. The use of corticosteroids may be indicated. Everolimus may be reintroduced at a daily dose approximately 50% lower than the dose previously administered.

For cases of grade 3 non-infectious pneumonitis, interrupt everolimus until resolution to less than or equal to grade 1. Everolimus may be re-initiated at a daily dose approximately 50% lower than the dose previously administered depending on the individual clinical circumstances. If toxicity recurs at grade 3, consider discontinuation of everolimus. For cases of grade 4 noninfectious pneumonitis, everolimus therapy should be discontinued. Corticosteroids may be indicated until clinical symptoms resolve.

For patients who require use of corticosteroids for treatment of non-infectious pneumonitis, prophylaxis for pneumocystis jirovecii pneumonia (PJP) may be considered.

Guidelines for management of non-infectious pneumonitis suspected to be associated with everolimus and dose modification instructions have been provided in [Table 6-4](#).

6.3.2 Infections

Everolimus has immunosuppressive properties and may predispose patients to bacterial, fungal, viral or protozoan infections, including infections with opportunistic pathogens. Localized and systemic infections, including pneumonia, other bacterial infections, invasive fungal infections, such as aspergillosis, or candidiasis, or pneumocystis jirovecii pneumonia (PJP) and viral infections including reactivation of hepatitis B virus, have been described in patients taking everolimus. Some of these infections have been severe (e.g. leading to sepsis, respiratory or hepatic failure) and occasionally have had a fatal outcome.

Physicians and patients should be aware of the increased risk of infection with everolimus. Treat pre-existing infections prior to starting treatment with everolimus. While taking everolimus, be vigilant for symptoms and signs of infection; if a diagnosis of infection is made, institute appropriate treatment promptly and consider interruption or discontinuation of everolimus.

Patients with positive results of HBV-DNA and/or HBsAg at screening should begin a prophylaxis treatment for 1-2 week prior to beginning everolimus therapy. Patients should have HBV-DNA monitored frequently throughout the course of everolimus therapy for signs of hepatitis reactivation.

If a diagnosis of invasive systemic fungal infection is made, discontinue everolimus and treat with appropriate antifungal therapy.

Cases of *Pneumocystis jirovecii* pneumonia (PJP), some with a fatal outcome, have been reported in patients who received everolimus. PJP may be associated with concomitant use of corticosteroids or other immunosuppressive agents. Prophylaxis for PJP should be considered when concomitant use of corticosteroids or other immunosuppressive agents are required.

[figure not shown]
6.3.3 Management of Hepatitis reactivation/flare

6.3.3.1 Monitoring and prophylactic treatment for hepatitis B reactivation

Table 6-5 provides details of monitoring and prophylactic therapy according to the screening results of viral load and serologic markers testing. If the patient is already known to have a chronic infection with HBV and is taking anti-HBV medication, the site does not have to wait for the screening HBV results prior to enrolment in the study.

Table 6-5 Actions recommended base on hepatitis B screening results

	Result				
HBV-DNA	+	+ or -	-	-	-
HBsAg	+ or -	-	-	-	-
HBsAb	+ or -	+ or -	+ and no prior HBV vaccination	+ or -	- or + with prior HBV vaccination
HBcAb			+ or -	+	-
Recommendation	Prophylaxis treatment should be started at least 1 week prior to first dose of study drug. Monitor HBV-DNA approximately every 6 weeks (from Visit 2 and onwards)		No prophylaxis Monitor HBV-DNA approximately every 3 weeks (from Visit 2 and onwards)		No specific action

Antiviral prophylaxis therapy should continue for at least 4 weeks after last dose of study drug. The first HBV-DNA result would be regarded as screen visit.

For hepatitis B reactivation, definition and management guidelines, see [Table 6-6](#) Guidelines for management of hepatitis B.

Table 6-6 Guidelines for management of hepatitis B

HBV reactivation (with or without clinical signs and symptoms)*	

For patients with baseline results: Positive HBV-DNA OR Positive HBsAg
 
-----
 
Reactivation is defined as: [Increase of 1 log in HBV-DNA relative to baseline HBV-DNA value OR new appearance of measurable HBV-DNA]
	
Treat: Start a second antiviral AND Interrupt study drug administration until resolution: - ≤ baseline HBV-DNA levels
 
If resolution occurs within 28 days, study drug should be re-started at one dose lower, if available. (see Table 6-2- Study drug dose reductions) If the patient is already receiving the lowest dose of study drug according to the protocol, the patient should restart at the same dose after resolution. Both antiviral therapies should continue at least 4 weeks after last dose of study drug. If resolution occurs > 28 days, patients should discontinue study drug but continue both antiviral therapies at least 4 weeks after last dose of study drug.


For patients with baseline results: Negative HBV-DNA and HBsAg AND [Positive HBs Ab (with no prior history of vaccination against HBV), OR positive HBc Ab]
 
-----
 
reactivation is defined as: New appearance of measurable HBV-DNA
	
Treat Start first antiviral medication AND Interrupt study drug administration until resolution: ≤ undetectable (negative) HBV-DNA levels If resolution occurs within 28 days, study drug should be re-started at one dose lower, if available. (see Table 6-7 - Study drug dose reductions) If the patient is already receiving the lowest dose of study drug according to the protocol, the patient should restart at the same dose after resolution. Antiviral therapy should continue at least 4 weeks after last dose of study drug. If resolution occurs > 28 days, patients should discontinue study drug but continue antiviral therapy at least 4 weeks after last dose of study drug.

* All reactivations of hepatitis B are to be recorded as grade 3 (CTCAE v 3.0 Metabolic Laboratory/Other: Viral Re-activation), unless considered life threatening by the investigator; in which case they should be recorded as grade 4 (CTCAE v 3.0 Metabolic Laboratory/Other: Viral Re-activation). Date of viral reactivation is the date on which the rise or reappearance of HBV- DNA was recorded.
	

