After eligibility is confirmed (all inclusion/exclusion criteria verified), patients can be enrolled. All screening evaluations (including screening for hepatitis B and C) should be completed within 21 days prior to the first dose of the study drugs (Treatment Day 1).

Screening for hepatitis B

During the screening period, the following three categories of patients should be tested for hepatitis B viral load and serologic markers, that is, HBV-DNA, HBsAg, HBsAb, and HBcAb:

1. All patients who currently live in (or have lived in) Asia, Africa, Central and South America, Eastern Europe, Spain, Portugal, and Greece for more than 6 months.

2. Patients with any of the following risk factors:
 - Known or suspected past hepatitis B infection,
 - Blood transfusion(s) prior to 1990,
 - Current or prior IV drug users,
 - Current or prior dialysis,
 - Household contact with hepatitis B infected patient(s),
 - Current or prior high-risk sexual activity,
 - Body piercing or tattoos,
 - Mother known to have hepatitis B,
 - History suggestive of hepatitis B infection, e.g., dark urine, jaundice, right upper quadrant pain.
3. Additional patients at the discretion of the investigator.

Patients with positive HBV-DNA or HBsAg at screening must initiate prophylaxis with appropriate antiviral medication at least one week prior to treatment start (Treatment Day 1). The management guidelines are provided according to the results of the baseline assessment of viral load and serological markers for hepatitis B (see [Section 6.3.3.1](#)).

Screening for hepatitis C

Patients with any of the following risk factors for hepatitis C should be tested using quantitative RNA-PCR

- Known or suspected past hepatitis C infection (including patients with past interferon ‘curative’ treatment),
- Blood transfusions prior to 1990,
- Current or prior IV drug users,
- Current or prior dialysis,
- Household contact of hepatitis C infected patient(s),
- Current or prior high-risk sexual activity,
- Body piercing or tattoos,
- Additional patients at the discretion of the investigator.

The management guidelines are provided according to the results of the baseline assessment of hepatitis C viral load (see [Section 6.3.3.2](#)).

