If bone lesions have been previously irradiated, at least one lesion must have clearly progressed since the radiotherapy by CT, MRI or X-ray for trial entry (in the absence of measurable disease).
7. Adequate bone marrow and coagulation function as shown by:
- Absolute neutrophil count (ANC) $\geq 1.5 \times 10^9/L$
 - Platelets $\geq 100 \times 10^9/L$
 - Hemoglobin (Hgb) ≥ 9.0 g/dL
 - INR ≤ 2 .
8. Adequate liver function as shown by:
- Serum aspartate aminotransferase (AST) and alanine aminotransferase (ALT) ≤ 2.5 ULN (or ≤ 5 if hepatic metastases are present)
 - Total serum bilirubin $\leq 1.5 \times$ ULN ($\leq 3 \times$ ULN for patients known to have Gilbert Syndrome).
9. Adequate renal function as shown by serum creatinine $\leq 1.5 \times$ ULN.

10. Fasting serum cholesterol ≤ 300 mg/dl or 7.75 mmol/L and fasting triglycerides $\leq 2.5 \times$ ULN. Treatment with statins may be initiated or adjusted as needed to meet these values before enrolment.
11. ECOG Performance Status ≤ 2 .
12. Adequate organ function at the discretion of the investigator.
13. Patients with positive HBV-DNA and/or HBsAg at screening must initiate prophylaxis with appropriate antiviral medication at least one week prior to treatment start.
14. Signed informed consent obtained before any trial related activity and according to local guidelines.

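### Table 6-5 as printed has no column for an HBV-DNA-negative, HBsAg-positive patient and gives opposing recommendations for patients negative on both tests

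*Protocol*

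**What the plan says.** Four places in the Protocol's text set the same trigger for antiviral prophylaxis: either marker positive. Inclusion criterion 13 (Section 5.1) reads "Patients with positive HBV-DNA and/or HBsAg at screening must initiate prophylaxis with appropriate antiviral medication at least one week prior to treatment start". Section 4.1 says "Patients with positive HBV-DNA or HBsAg at screening must initiate prophylaxis with appropriate antiviral medication" and refers sites to Section 6.3.3.1 for management by test result. Sections 6.3.2 and 7.1.1 repeat the trigger.

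Table 6-5 in Section 6.3.3.1 has five result columns:

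| Row | Col 1 | Col 2 | Col 3 | Col 4 | Col 5 |
|---|---|---|---|---|---|
| HBV-DNA | + | + or - | - | - | - |
| HBsAg | + or - | - | - | - | - |
| HBsAb | + or - | + or - | + "and no prior HBV vaccination" | + or - | - "or + with prior HBV vaccination" |
| HBcAb | (blank) | (blank) | + or - | + | - |

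Columns 1 and 2 carry "Prophylaxis treatment should be started at least 1 week prior to first dose of study drug", with HBV-DNA about every 6 weeks. Columns 3 and 4 say no prophylaxis, with HBV-DNA about every 3 weeks. Column 5 says "No specific action".

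Table 6-6, on reactivation, splits patients differently. Its first group is headed "For patients with baseline results: Positive HBV-DNA OR Positive HBsAg", and a second antiviral is added. Its second group is negative on both, with antibody evidence of past infection, and a first antiviral is started.

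**The concern.** The text and Table 6-6 divide patients into those with either marker positive and those with both negative. Table 6-5, the table sites are sent to for the action, does not follow that division. Read literally, it omits one group that the entry criterion singles out and gives another group two incompatible recommendations.

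The setting makes this matter. Safety is the primary objective. The Protocol reports hepatitis B reactivation with fatal outcome (Section 1.2.1.2.2), and Table 6-6 has every reactivation recorded as grade 3, or grade 4 if life-threatening. Reactivation is defined by HBV-DNA, so the monitoring interval also bears on when it is detected. Section 4.1 says that patients who live, or have lived for more than 6 months, in Asia or Africa, among other regions, should be tested. On the SAP's country list that covers 12 of 13 countries, all but Australia.

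**Working it through.** No sample size or error rate is involved. The check is whether each result pattern leads to exactly one recommendation.

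**Step 1. The four HBV-DNA and HBsAg combinations against Table 6-5 as printed.**

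| HBV-DNA | HBsAg | Trigger in the text | Columns matched | Result |
|---|---|---|---|---|
| + | + | prophylaxis | 1 | consistent |
| + | - | prophylaxis | 1 and 2, same action | consistent |
| - | + | prophylaxis | none | no entry |
| - | - | none | 2, plus at least one of 3 to 5 | opposing actions |

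The third row follows from two rows of the table alone. HBsAg + is admitted only in column 1, and column 1 requires HBV-DNA +.

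**Step 2. The double-negative patients by antibody result.** The blank HBcAb cells in columns 1 and 2 are read as any result.

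| HBsAb | HBcAb | Columns | Recommendations |
|---|---|---|---|
| - | + | 2, 4 | prophylaxis; no prophylaxis, 3-weekly |
| - | - | 2, 5 | prophylaxis; no specific action |
| +, unvaccinated | + | 2, 3, 4 | prophylaxis; no prophylaxis, 3-weekly |
| +, unvaccinated | - | 2, 3 | prophylaxis; no prophylaxis, 3-weekly |
| +, vaccinated | + | 2, 4 | prophylaxis; no prophylaxis, 3-weekly |
| +, vaccinated | - | 2, 5 | prophylaxis; no specific action |

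All six patterns carry two incompatible recommendations. One of them sits in three columns, but columns 3 and 4 share an action.

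**Step 3. Where the faults come from.** The HBV-DNA-positive part of column 2 is already covered by column 1 with the same action. As printed, column 2 therefore adds only double-negative patients. Rerunning the enumeration with a + in the HBsAg cell of column 2 leaves no pattern without an action and none with two different actions. This locates the inconsistency in one cell. It does not decide which passage is clinically right.

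**Step 4. Whether other text fills the gap.** For the HBV-DNA-negative, HBsAg-positive patient, the text supplies the prophylaxis trigger. It does not supply the interval: Section 6.3.2 asks only for frequent HBV-DNA monitoring, and Table 7-1 and Section 7.2.3.5 give 3 to 6 weeks when required. The choice between 6-weekly and 3-weekly is made only in Table 6-5. For double-negative patients with antibody evidence, Table 6-6 starts a first antiviral on reactivation. That presupposes none is running and contradicts column 2.

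**The case against.** The strongest objection is provenance. Both faults hang on one sign in a table read from a PDF, with merged recommendation cells and blank HBcAb cells. If the source differs there, both disappear. That stands as a reason to check the source first. It does not dispose of the point, because the HBsAg row has five entries aligned with the rows around it and nothing in the text shows a reading fault.

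A second objection is that a careful reader could work out the intent. The text ties prophylaxis to a positive marker, columns 3 to 5 are specific to double-negative patients, and Table 6-6 agrees with them. This is fair, but a site should not have to overrule one column of the action table by inference.

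Several stronger readings are tempting and are not supported:

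- A reader might infer that sites have no prophylaxis instruction for the HBsAg-positive patient. They do, in four places. What is missing is the table entry and its monitoring interval.
- A reader might turn the pattern count into a share of patients. Patterns are not equally common, and the documents give no HBsAg or HBV-DNA prevalence. Enrolment of 400 is a ceiling. The Protocol gives 198 enrolled at 30 June 2014, with recruitment ending by 31 October 2014 at the latest.
- A reader might treat the blank HBcAb cells as an omission. They may be merged cells or lost in reading, so nothing is asked about them.
- A reader might expect Listing 18.6 alone to show whether prophylaxis was given. It holds test results and sample dates, with no antiviral data.

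**Conclusion.** The point holds for Table 6-5 as printed. The table omits the HBV-DNA-negative, HBsAg-positive patient and places every double-negative patient under opposing recommendations. It is inconsistent with inclusion criterion 13, Sections 4.1, 6.3.2 and 7.1.1, and Table 6-6.

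The size is logical rather than numerical: one combination of the two main markers has no entry, and one has two incompatible entries. The number of patients affected cannot be derived from the documents. No analysis set or method changes, and the safety analysis is descriptive. What is affected is the consistency of a safety instruction and of the monitoring behind a graded adverse event.

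Two assumptions remain. The HBsAg cell in column 2 is taken as correctly read. The blank HBcAb cells are taken as placing no restriction. The missing column does not depend on the second assumption, but the statement that every double-negative patient is affected does. No view is taken on which clinical rule is right.

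**What to change.** 1. Check the HBsAg entry in column 2 of Table 6-5 against the source document.
2. If it stands, reconcile Table 6-5 with inclusion criterion 13, Sections 4.1, 6.3.2 and 7.1.1, and Table 6-6, so that each result pattern leads to exactly one recommendation, including one monitoring interval where monitoring applies. The sponsor's medical team settles the clinical content.
3. For enrolled patients who were HBV-DNA negative and HBsAg positive at screening, compare the results in Listing 18.6 with antiviral start dates in the medication listings (10.1 and 10.2) and with the recorded inclusion 13 status in Listing 3. Listing 18.6 has no visit column, so the screening sample has to be identified by date. Review any inconsistency under the existing inclusion-criteria category of Table 1.6.

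The cost is a correction to one table, by written amendment as Section 12.1 requires, and a cross-check of listings already planned. No new tests or data collection are needed. With recruitment due to end by 31 October 2014, the benefit lies in clear guidance for patients still on treatment and in a review of those already enrolled.

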7.2.3.5 Hepatitis B viral load and markers, hepatitis C viral load

HBV-DNA, HBsAg, HBsAb, HBcAb and HCV-RNA will be measured at screening. Significant findings must be recorded as Relevant Medical History / Current Medical Conditions.

[figure not shown]
These assessments will be repeated every 3-6 weeks during the treatment period when required. Results will be recorded in the CRF. Hepatitis reactivation or flare will be managed according to guidelines presented in [Section 6.3.3](#), and will be recorded on the Adverse Events CRF.

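### Table 6-6 restarts study drug after hepatitis B reactivation on viral load alone, with no exception for a life-threatening (grade 4) event; this conflicts with Table 6-4 and Section 6.2.1, and no text says which rule prevails

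*Protocol*

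**What the plan says.** Two places in the protocol send the reader to the hepatitis guidance. Section 6.3.3.1 says "For hepatitis B reactivation, definition and management guidelines, see" Table 6-6, and Section 7.2.3.5 says "Hepatitis reactivation or flare will be managed according to guidelines presented in" Section 6.3.3.

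The heading of Table 6-6 covers reactivation whether or not there are clinical signs. It has two cells:

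- **First cell** (HBV-DNA or HBsAg positive at baseline): add a second antiviral and interrupt study drug until HBV-DNA is at or below baseline.
- **Second cell** (both negative at baseline, but HBcAb positive, or HBsAb positive without vaccination): start a first antiviral and interrupt until "undetectable (negative) HBV-DNA levels".

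Both cells then give the same instruction: "If resolution occurs within 28 days, study drug should be re-started at one dose lower, if available". For a patient already at the lowest dose, "the patient should restart at the same dose after resolution". The only trigger for discontinuation in the table is resolution later than 28 days. Antiviral therapy continues for at least 4 weeks after the last dose of study drug.

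The footnote grades every reactivation as 3, "unless considered life threatening by the investigator; in which case they should be recorded as grade 4". It governs recording and does not change the dosing action.

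For the dose steps, the first cell says "see Table 6-2- Study drug dose reductions" and the second says "see Table 6-7 - Study drug dose reductions".

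**The concern.** A life-threatening reactivation whose viral load falls within 28 days meets the Table 6-6 condition for restart. A site that follows that table literally would give an immunosuppressant again after such an event, without being asked whether the liver or the patient has recovered. A site that turns to Table 6-4 would find the opposite instruction under grade 4 other non-hematologic toxicities.

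What is at stake is patient safety. The protocol's safety background (Section 1.2.1.2.2) reports hepatitis B reactivation with fatal outcome on everolimus. Antiviral prophylaxis before treatment (Section 4.1) is required only for patients with positive HBV-DNA or HBsAg at screening. The antibody-positive group in the second restart cell gets none under Table 6-5, although HBV-DNA is monitored about every 3 weeks. The setting is relevant too. The SAP lists 13 countries, nine that it classes as Asian plus Morocco, South Africa, Tunisia and Australia. If the SAP's Asian class is taken as the protocol's Asia, 9 + 3 = 12 of the 13 lie in regions where Section 4.1 requires hepatitis B testing of residents.

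**Working it through.** The protocol states no figure to reproduce, so the check is a comparison of texts followed by simple dose arithmetic.

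**1. Is there a grade 4 exception for hepatitis B?** Restart cells in Table 6-6: 2. Cells with a grade 4 exception: 0. Cells with a clinical or liver-function criterion for resolution: 0. Sections 6.2, 6.3.2, 6.5, 7.1.4 and 7.2.3.5 contain no hepatitis-B-specific exception either.

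**2. What do the neighbouring rules say?**

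| Text | Rule |
|---|---|
| Table 6-4, grade 4 (pneumonitis, stomatitis, other non-hematologic, metabolic) | Discontinue everolimus in 4 of 4 rows |
| Section 6.2.1 | After a toxicity interruption, resume only if recovery to grade 1 or less takes under 4 weeks; dose then depends on type and grade of toxicity |
| Table 6-3 (hematologic) | ANC below 500/mm³, platelets below 50000/mm³ and febrile neutropenia: restart at the next lower dose after recovery |
| Table 6-6 | Restart if HBV-DNA resolves within 28 days; no grade condition |

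The row for other non-hematologic toxicities excludes only metabolic events, so a grade 4 reactivation can be read as falling under it. The same event then has two opposite instructions. The time limit does not separate them: 28 / 7 = 4 weeks, which is also the general limit in Section 6.2.1.

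**3. Does Section 6.2.1 settle it?** Not clearly. Its text points to Tables 6-3 and 6-4 for the procedure and does not mention Table 6-6, which sets its own test of resolution. Because the Table 6-6 footnote fixes the grade by rule (3, or 4 if life-threatening), a site could also take viral resolution as recovery of the event, whatever the state of the liver.

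**4. What dose does each rule give after a resolved grade 4 reactivation?** Levels are from Table 6-2; 5 mg every other day averages 5 / 2 = 2.5 mg/day.

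| Dose at event | Table 6-6 restart dose | Ratio | Table 6-4, grade 4 |
|---|---|---|---|
| 10 mg/day | 5 mg/day | 5 / 10 = 50% | 0 |
| 5 mg/day | 2.5 mg/day | 2.5 / 5 = 50% | 0 |
| 2.5 mg/day | 2.5 mg/day | 2.5 / 2.5 = 100% | 0 |

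These ratios show how far apart the two instructions are. They do not measure risk.

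**5. Table reference.** Table 6-7 is the hepatitis C table, and its only action is to discontinue study drug. The dose steps are in Table 6-2, as the first cell says. The second cell's reference is a clerical error.

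**The case against.** The strongest reply is that the protocol, read as a whole, already protects the patient. Section 6.2.1 requires recovery to grade 1 or less. Section 6.2.2 requires at least weekly follow-up until the event resolves or returns to grade 1, and Section 7.2.3.2 requires weekly biochemistry until recovery when a non-hematologic toxicity of grade 2 to 4 leads to a dose change. Section 6.5 lists unacceptable adverse events and investigator discretion as grounds to stop. Section 6.3.2 advises considering interruption or discontinuation when infection is diagnosed. Table 6-6 itself makes antiviral treatment mandatory, so a restart happens under cover and with viral load controlled. The tables are also described as guidelines.

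Most of this stands. A reader might infer that the restart instruction is wholly unqualified, or that the protocol has no stop rule for a grade 4 reactivation. The documents do not support that: Section 6.2.1 qualifies resumption in general terms, and Table 6-4 can be read to supply the stop rule. A reader might also infer that grade 4 toxicity always ends everolimus in this protocol. Table 6-3 shows otherwise for severe hematologic toxicity. Nor is the hepatitis C table, which stops study drug for every flare, a like-for-like comparator: a flare requires ALT elevation as well as a viral rise, while hepatitis B reactivation can be defined on viral load alone.

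What the reply does not remove is the conflict. The general provisions permit a site to stop; the specific table tells it to restart. No sentence ranks one above the other, and the reminder to use medical judgement is attached to Table 6-3, not to Table 6-6.

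**Conclusion.** The point holds as a conflict between a specific table and the protocol's general rules. Table 6-6 directs a restart after any hepatitis B reactivation that resolves virologically within 28 days, including one its own footnote grades as life-threatening, and it sets no clinical-recovery condition. Table 6-4 and Section 6.2.1 point the other way, and precedence is not stated.

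The size is modest. The documents give no frequency for grade 4 reactivation; I assume it is rare and claim no patient count. No endpoint or analysis is affected. The conclusion rests on reading the Table 6-4 row for other non-hematologic toxicities as capable of covering a reactivation, and on the absence of any ranking between the tables. It is a worthwhile patient-safety clarification and does not threaten the trial.

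**What to change.** 1. In both restart cells of Table 6-6, state that a reactivation recorded as grade 4 leads to permanent discontinuation of study drug. The antiviral therapy already specified in that cell (both antivirals in the first cell) continues for at least 4 weeks after the last dose.
2. For all other reactivations, make restart conditional on HBV-DNA resolution and on the Section 6.2.1 condition that any associated clinical or liver toxicity has recovered to grade 1 or less. Without this, grade 3, the default grade, would still restart on viral load alone.
3. In the Table 6-4 row for other non-hematologic toxicities, refer hepatitis B reactivation to Table 6-6, so that one rule applies.
4. Clerical: in the second restart cell, change the reference from Table 6-7 to Table 6-2.

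This is a cheap improvement: a few lines of text, with the recovery check drawing on monitoring the protocol already requires. Section 12.1 requires a written amendment, and the change can go into the next one. The downside is that a rare patient with a resolved grade 4 reactivation, or with slow clinical recovery, would not restart everolimus.
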